This document is a protocol for a human research study. This study is to be conducted in compliance with this research protocol, as well as according to US and international standards of Good Clinical Practice (FDA Title 21 part 312 and International Conference on Harmonization guidelines), applicable government regulations, and institutional research policies and procedures.

2.1 Background

Combustible cigarette smoking results in the rapid delivery of nicotine, contributing to smoking persistence, as well as long-term exposure to numerous toxins and carcinogens. Heat-not-burn (HNB) tobacco products are an emerging nicotine delivery innovation designed to deliver nicotine without the toxins associated with combustion. In 2019, the FDA approved the sale of IQOS, the first HNB tobacco product available in the U.S. Manufactured by Philip Morris International, IQOS is a rechargeable electronic device that produces a nicotine-containing aerosol by heating a disposable tobacco stick called HEETS or HeatSticks.

[figure not shown]
Since entering the market in 2014, global sales of IQOS have increased with millions of users across 50 countries. In 2017, 1 in 10 smokers in the U.S. was aware of HNB tobacco products such as IQOS. Awareness increased by 33% across the following 12 months. Among those aware, 18% had ever used IQOS, while almost 9% were current users, a 50% increase from the previous year. Current smokers had six times the odds of ever use compared to never smokers, suggesting the potential for dual product use. Tobacco scientists and market analysts forecast rapid growth in IQOS sales in the U.S. over the next few years.

While demand for IQOS is expected to increase among cigarette smokers, the lack of scientific studies evaluating the impact of IQOS use on cigarette smoking behaviors renders us unable to predict how an increase in IQOS sales will affect public health and regulatory actions. The proposed research will examine: 1) whether cigarette smokers switch completely to IQOS or dual-use two tobacco products; 2) whether IQOS use affects smokers' motivation to quit smoking cigarettes; and 3) how risk perceptions of IQOS and IQOS use impact cigarette smoking behaviors.

The proposed study will fill gaps in the evidence base by recruiting combustible cigarette smokers to a 21-day protocol using a within-subjects design. Baseline smoking rate will be established during days 1-5. After overnight cigarette smoking abstinence, laboratory visits on days 6 and 7 will assess IQOS-associated craving relief, withdrawal relief, subjective reward, and the reinforcing value of IQOS relative to combustible cigarettes. Participants will switch from cigarette smoking to IQOS use for the following 14 days (days 8-21). Participants will collect their spent cigarette filters and their used IQOS HeatSticks daily in order to assess consumption of cigarettes per day (cpd) and tobacco HeatSticks per day (spd). The primary outcome measure will be the longitudinal daily count of cigarettes from baseline to the end of the 14-day IQOS switch phase. Changes in motivation to quit smoking will be a secondary outcome.

3 Study Objectives

Aim 1: To evaluate the effects of IQOS use on cigarette smoking behaviors.

CONFIDENTIAL

This material is the property of the University of Pennsylvania. Do not disclose or use except as authorized in writing by the study sponsor

H1a: IQOS use will decrease the number of cigarettes smoked per day relative to baseline. We do not expect IQOS to replace all cigarettes, and we will measure IQOS only use (complete switching), cigarette smoking only, and dual use.

H1b: The reduction in number of cigarettes smoked per day will be associated with the number of IQOS sticks used.

H1c: IQOS use will decrease smokers' motivation to quit cigarette smoking.

Aim 2: To examine which subjective and objective effects of IQOS predict cigarette smoking.

H2: Participants with lower IQOS risk perceptions, greater craving and withdrawal relief, greater IQOS subjective reward, and a higher relative reinforcing value of IQOS will smoke fewer cigarettes per day during the 14-day switching phase.

This will be the first independent and prospective study to examine the subjective, objective, and behavioral effects of IQOS use on cigarette smoking behaviors (i.e., switching, dual use and smoking cessation-related behaviors). As the only HNB tobacco product available in the US, demand for IQOS presents tobacco control challenges such as encouraging the long-term use of combustible cigarettes and foregoing the benefits of cessation, while risking the unknown effects of dual use. A greater understanding of IQOS use and its relationship to cigarette smoking will be fundamental to address these challenges and to inform appropriate public health and regulatory actions. The findings will directly address CTP's Rapid Response priority #4 (Behavior) to assess the likely impact of heated tobacco products on cigarette smoking behaviors (i.e., switching, use, dual use and smoking cessation-related behaviors).

4 Study Design

4.1 General Design

We propose to conduct a within-subjects study of the impact of IQOS use on smoking behavior among 160 combustible cigarette smokers. Eligible smokers will participate in 8 visits across a 21-day protocol. Participants who are eligible based on telephone screening will complete an in-person Intake Visit (**day 0**). Those eligible will complete measures of demographics, smoking history, and motivation to quit smoking. Baseline cigarette smoking rate will be established during **days 1-5** by instructing participants to smoke as usual for the following five days (**days 1-5**), while collecting their spent cigarette filters each day. Participants will return to the lab on **day 6** after overnight smoking abstinence (CO < 10). Participants will be required to use the IQOS device in the lab, then complete an assessment of IQOS-associated craving relief, withdrawal relief, subjective rewarding value of IQOS, and IQOS-associated risk perceptions. Participants will also return to the Center on **day 7** after overnight smoking abstinence (CO value 50% of Intake visit's CO value) for an assessment of the Relative Reinforcing Value of IQOS (RRVI) after required use of the IQOS device in the lab. **See Figure 1.**

Participants will then be instructed to use IQOS (versus cigarettes) for the following 14 days (**days 8-21**). Participants will collect their used cigarette filters and their used IQOS HeatSticks daily in order to assess consumption of cigarettes per day and sticks per day. Participants will return to the Center on days 11, 14, 17, and 21 to have their carbon monoxide (CO, exhaled breath) measured, and to return their used tobacco sticks and any spent cigarette filters. Cigarette smoking status will be assessed via self-report, spent cigarette filters, and biochemically verified (CO value 50% of Intake visit's CO value). Changes in motivation to quit smoking will be measured at study end, and all remaining used sticks and spent cigarette filters will be returned on Day 22.

On Day 22, participants will be: (1) informed of the lack of data supporting IQOS as a smoking cessation aid or harm reduction tool; (2) cautioned on the likelihood of dual use and the risks

CONFIDENTIAL

This material is the property of the University of Pennsylvania. Do not disclose or use except as authorized in writing by the study sponsor

associated with dual use; (3) advised to either quit using IQOS or to quit smoking cigarettes if they are using both; and (4) referred to a smoking cessation program if interested in quitting smoking. The **primary outcome** measure will be the longitudinal daily count of cigarettes from baseline to the end of the 14-day IQOS switch phase. Changes in motivation to quit smoking from baseline to study end will be a **secondary outcome**.

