5.4 Exclusion Criteria

Subjects who present and/or self-report with the following criteria will not be eligible to participate in the study:

Smoking Behavior

CONFIDENTIAL

This material is the property of the University of Pennsylvania. Do not disclose or use except as authorized in writing by the study sponsor

1. Regular use of nicotine containing products other than cigarettes (e.g. chewing tobacco, snuff, snus, cigars, e-cigs, etc.). Participants agreeing to abstain from using nicotine containing products other than cigarettes for the duration of study will be considered eligible.
2. Current enrollment or plans to enroll in a smoking cessation program over the duration of the study (i.e. 21 days/3 weeks).
3. Provide a CO breath test reading less than 10 ppm at Intake.

Alcohol and Drug

1. History of substance abuse (other than nicotine dependence) in the past 12 months and/or currently receiving medical treatment for substance abuse. Counseling and support groups (e.g. Alcoholics Anonymous and Narcotics Anonymous) will not be considered medical treatment for the purposes of this protocol.
2. Current alcohol consumption that exceeds 20 standard drinks/week.
3. Breath alcohol reading (BrAC) greater than .000 at Intake.

Medical

1. Women, including all individuals assigned as "female" at birth, who are pregnant, breast feeding, or planning a pregnancy over the duration of the study period.
2. Serious or unstable disease within the past year (e.g. cancer, heart disease). Applicable conditions will be evaluated on a case-by-case basis by the Principal Investigator.

Psychiatric

1. Lifetime history of schizophrenia or psychosis.
2. Lifetime history or current diagnosis of active major depression. Participants who maintain a diagnosis of major depression who have not experienced any major depressive episodes in the past 6 months and are stable on antidepressant medication(s) are eligible to participate.
3. Lifetime history of a suicide attempt.

General Exclusion

1. Past, current, anticipated, or pending enrollment in another research program over the study period that could potentially impact subject safety, study data, and/or the study design as determined by the Principal Investigator.

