6. Female participants are advised that participation of pregnant women in this study is prohibited and that they may withdraw at any time.
7. Have height and weight measured.
8. Perform a BrAC assessment to control for alcohol consumption.
9. Participants with a BrAC greater than 0.000 at Intake Visit will be ineligible.

CONFIDENTIAL

This material is the property of the University of Pennsylvania. Do not disclose or use except as authorized in writing by the study sponsor

10. Perform a CO breath assessment and collect self-report smoking behavior over the past 24 hours to control for prior tobacco exposure.
11. Participants with a CO reading less than 10 ppm will be deemed ineligible.
12. Be asked questions about use of marijuana, other tobacco products (besides cigarettes), or vaping of any substance including tobacco/nicotine or other drugs in the past month.
13. Complete a Medical History Form with a member of the research team to review for applicable contraindications, including psychiatric exclusions, previously listed under Inclusion and Exclusion Criteria (section 4.3 and 4.4).
14. Complete a baseline concomitant medication review (if applicable).
15. Complete questionnaires:
16. Demographics
17. Smoking History (e.g., duration, rate, regular and/or menthol)
18. Nicotine Dependence (FTND)
19. Motivation to quit smoking (Contemplation Ladder)
20. Provide instructions to smoke as usual for the first five days of the study protocol (assessment of baseline smoking rate).
21. Be provided with five date-stamped zipped baggies by the research staff.
22. Review a written instruction card for the collection and storage of used cigarette filters with the research staff.
23. Be instructed to engage in overnight smoking abstinence (10-hours) the night of Day 5 in preparation for the Day 6 Visit.
24. Tentatively schedule study visits with a member of the research team.

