assessment will inquire about any event(s) or symptom(s) experienced since the last in-person visit. If a participant reports a symptom or medical event, they will be asked to rate the severity of the event utilizing the following severity scale: 0 (None=No Concerns), 1 (Mild=Issue does not interfere with usual daily activities), 2 (Moderate=Issue does interfere with some activities), and 3 (Severe=No normal activities are possible). See section 8.2.1: AE Collection Methods for further details.

Carbon Monoxide (CO) will be measured using a Vitograph CO monitor (Lenexa, KS). A CO > 5 is indicative of combustible cigarette smoking [25,45,46]. HNB products are expected to result in significantly lower increases in CO compared to a combustible cigarettes [47]. Five minutes of IQOS use did not result in clinically significant increases in CO (0.3 ppm) after overnight abstinence compared to five minutes of combustible cigarette [27]. We will include CO as a covariate in our statistical models.

Concomitant Medications: At the Intake Visit, participants will be asked to list all medications (prescription or non-prescription) and NRTs currently taken and/or recently discontinued (within the past 14 days) as a baseline collection. All information will be collected on a Concomitant Medication Log that will be maintained within the participant's study chart. At every subsequent in-person visit, participants will be asked if they have taken any additional medications (prescription or non-prescription), NRTs, and/or changed the dosage or stopped taking any previously reported medications since their last in-person visit. Participants who report taking contraindicated medication(s) over the course of the study period may only remain eligible if the Principal Investigator determine that the contraindicated medication(s) did not impact the study design, data quality, and/or participant safety and welfare.

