7.4.3 Outcome variables

Cigarette Consumption (primary outcome): The primary outcome is the longitudinal daily count of cigarettes from Intake to the end of the IQOS switch phase. Daily cigarette consumption will be determined by counting the daily spent cigarette filters returned for each of the 14 days (days 8-21).

Motivation for smoking cessation (secondary outcome): The contemplation ladder will be used to assess readiness to consider smoking cessation. The contemplation ladder is designed to measure a smoker's position on an 11-point scale (0-10) range, from having no thought of quitting to taking action to quit, and has been successfully employed in several diverse smoking populations [60, 62]. We will assess changes in quitting motivation from baseline to day 21 (end of study).

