The primary outcome is a daily count variable, the number of cigarettes smoked each day. The distribution of cigarettes smoked per day is expected to be over-dispersed (and perhaps zero inflated), because of the study instructions for participants to switch to IQOS heat-sticks for a 14-day period, and the expectation that the majority of participants will have various levels of dual use. The number of IQOS HeatSticks used each day is also a count variable. Participants may have days where they only use IQOS HeatSticks, only smoke cigarettes, and days where they use both. We will accomplish the measurement portion of Aim 1 by summarizing the daily frequencies of cigarettes only, partial switching, and complete switching. Distributional assumptions of all regression methods will be examined in the data set ahead of the analysis to ensure that the best and most representative error model is used. We will examine demographic and other variables for any association with the outcomes or predictors. Those found to be

CONFIDENTIAL

This material is the property of the University of Pennsylvania. Do not disclose or use except as authorized in writing by the study sponsor

associated with outcomes ($p=0.2$) will be included in the model either to correct for confounding or to control error.

The goal of Aim 1 is to evaluate the effects of IQOS use on cigarette smoking behaviors. For the primary analysis, we will analyze the longitudinal counts of cigarettes using mixed models (Gaussian or negative binomial as appropriate). The model will include predictors of time (continuous or discrete), and study phase (baseline versus switch period). We will also include candidate controlling variables (demographic and clinical).

H.1.a. states that IQOS use will decrease the number of cigarettes smoked per day relative to baseline. We do not expect IQOS to replace all cigarettes, and we will measure the use of cigarette smoking only, dual use, and IQOS only use (complete switching). H.1.a. will be tested using the z-score corresponding to the contrast between baseline and switch periods (phase). **H.1.b.** states that the reduction in number of cigarettes smoked per day will be associated with the number of IQOS HeatSticks used. For H.1.b., we will add the daily IQOS use to the model predicting cigarette use, and test using the z-score corresponding to the daily IQOS HeatStick count by phase interaction.

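### The 50%-of-Intake CO rule for switch-phase smoking status does not say what a pass means, and a pass cannot separate IQOS-only use from dual use with reduced CO

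*Combined protocol and SAP*

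**What the plan says.** Section 4.1 describes the checks made at the Day 11, 14, 17 and 21 visits: "Cigarette smoking status will be assessed via self-report, spent cigarette filters, and biochemically verified (CO value 50% of Intake" visit's CO value). No comparison sign is printed, and nothing says what a participant who meets the value is then taken to be.

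Section 7.4.1 gives a different level for the same measure: "A CO > 5 is indicative of combustible cigarette smoking". It adds that the study product contributes little: "Five minutes of IQOS use did not result in clinically significant increases in CO (0.3 ppm", measured after overnight abstinence.

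The entry floor for CO is set twice. Section 5.4 excludes people who "Provide a CO breath test reading less than 10 ppm at Intake", and section 7.2.2 repeats it: "Participants with a CO reading less than 10 ppm will be deemed ineligible".

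H1a in section 3 undertakes that "we will measure IQOS only use (complete switching), cigarette smoking only, and dual use". Section 7.5 meets this by "summarizing the daily frequencies of cigarettes only, partial switching, and complete switching". For the primary outcome, section 7.4.3 states: "Daily cigarette consumption will be determined by counting the daily spent cigarette filters returned".

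Two further places concern CO. For the Day 6 visit, section 4.1 defines overnight abstinence as CO below 10, while section 7.2.3 defines it as 50% of the Intake value. Day 7 is 50% of Intake in both 4.1 and 7.2.4.

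**The concern.** CO is the only biochemical measure listed at the switch-phase visits. It is therefore the only outside check on the filters and reports behind the description of IQOS-only and dual use. That check has value because sections 7.2.5 to 7.2.8 ask for filters only if applicable, so an unreturned filter looks the same as a cigarette not smoked. Participants have also been told at Day 7 to switch completely, so some under-return is plausible (an inference, not something the protocol states).

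A limit set at half of each person's own Intake value measures reduction. Someone who cuts down and keeps smoking can meet it. If meeting it were read as biochemical support for no cigarette smoking, some readings that section 7.4.1 associates with smoking would count as that support. The description of complete switching would then look better corroborated than it is.

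**Working it through.** The plan gives no figure of its own on this point, so there is nothing to reproduce. The check is threshold arithmetic.

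**Inputs**
- Intake CO of at least 10 ppm (5.4, 7.2.2).
- Switch-phase limit: 50% of Intake CO (4.1). The operator is an assumption, taken as at or below (≤), with strictly below (<) as the variant.
- Smoking marker: CO > 5 (7.4.1), unit taken as ppm.
- Readings taken in whole ppm (assumption).

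**Step 1: the limit.** T = 0.5 × Intake CO. The smallest possible value is 0.5 × 10 = 5 ppm. T equals the marker at Intake 10 and exceeds it at every higher Intake value.

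**Step 2: readings that pass and yet exceed 5.** These are whole values c with 5 < c ≤ T, or 5 < c < T.

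| Intake CO | T | Pass and > 5, read as ≤ | Pass and > 5, read as < |
|---|---|---|---|
| 10 | 5 | none | none |
| 11 | 5.5 | none | none |
| 12 | 6 | 6 | none |
| 13 | 6.5 | 6 | 6 |
| 15 | 7.5 | 6–7 | 6–7 |
| 20 | 10 | 6–10 | 6–9 |
| 30 | 15 | 6–15 | 6–14 |
| 40 | 20 | 6–20 | 6–19 |

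The overlap starts at Intake 12 (13 if <) and widens with Intake CO.

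**Step 3: comparison with the entry floor.** A reading of 10 ppm satisfies the CO requirement for enrolment as a smoker. It passes when 10 ≤ 0.5 × Intake, that is from Intake 20 (from 21 if <, since 0.5 × 21 = 10.5).

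**Step 4: the other direction.** Under ≤, a failing reading exceeds T, and T is at least 5, so every failing reading is above the marker. Under <, the single exception is a reading of 5 at Intake 10. A fail therefore still argues against a claim of no smoking. The weakness lies in a pass.

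**Step 5: where the cut-off is used.**
- Primary outcome (7.4.3): filters are counted. No CO rule.
- Daily use classes (7.5): cigarettes only, partial and complete switching. No CO rule.
- Tests of H1a, H1b, H1c and H2 (7.5): model contrasts. No CO cut-off.
- Section 7.4.1 makes CO a covariate, which does not involve the 50% limit.

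**Step 6: the Day 6 rules.** CO below 10 passes readings 0–9. The 50% rule passes the same set only if 9 ≤ 0.5 × Intake < 10, that is at Intake 18–19 (at 19–20 if <). At Intake 15, readings 8–9 pass the rule in 4.1 and fail the rule in 7.2.3. At Intake 30, readings 10–15 (10–14 if <) do the reverse.

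**The case against.** The strongest reply is that nothing in the plan depends on the cut-off. Step 5 bears this out. Four spot readings also could not classify 14 days whatever the threshold. This stands, and it confines the point to how the use-status description is supported.

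The second reply is that the meaning of a pass is supplied by the reader. A reader might infer that people the protocol regards as smokers will be reported as biochemically verified non-smokers. The documents do not support that: section 4.1 defines no such category, promises no such report, and names self-report and filters beside CO. What can be said is conditional: if a pass is taken as support for no smoking, the two sections conflict.

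The third reply is that 5 ppm is a cited descriptive statement, not an operating rule of the study, and that indicative is weaker than diagnostic. The 0.3 ppm figure covers five minutes of use, not two weeks of free use. Both qualifications are fair. They leave the need to reconcile the sections, and they are a reason to use 5 ppm as a flag for discordance and not as a new classification of participants.

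Finally, THC-positive people may enrol (7.4.1, urine drug screen), so some readings above 5 may have another source. This stands as a limit on the fix.

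**Conclusion.** The concern holds in a limited form. The switch-phase rule lacks an operator and a stated meaning. On either natural operator, and if a pass is taken as support for no cigarette smoking, it admits readings above the protocol's own 5 ppm marker from Intake 12 upward (13 if <). A pass then does not separate IQOS-only use from dual use with reduced CO; a fail remains informative.

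The consequence is confined to the biochemical support for the IQOS-only and dual-use description. A reader might infer that the primary result or the test of H1a is compromised. It is not, because neither uses this limit. The protocol gives no Intake CO distribution, so the share of participants affected is unknown; the table lists possible readings, not people.

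The Day 6 contradiction between 4.1 and 7.2.3 is separate and does not depend on what a switch-phase pass means. The arithmetic rests on whole-ppm readings and on ppm as the unit of the 5 marker.

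**What to change.** 1. Reconcile sections 4.1 and 7.4.1. State the operator, and state what a pass and a fail each mean.
2. Do not describe a reading as verifying cigarette-free status on the 50% value alone. Keep that value, with its direction stated, as a descriptive measure of CO reduction.
3. For Days 11, 14, 17 and 21, report the number of visits with CO above 5 and zero filters in the date-stamped bags for a window fixed in advance, for example the visit day and the day before. Show the marijuana answers from the same visit beside it. Since 7.2.9 lets remaining filters come in on Day 22, make the count once all bags are in. Use self-reported smoking here only if it is actually recorded at these visits: 7.2.5 to 7.2.8 list no such item.
4. Reconcile the Day 6 abstinence rules in 4.1 and 7.2.3. This review does not choose between them.
5. As a clarification only, state the time point of the CO covariate. Section 7.4.1 names none, and Table 1 places CO under baseline covariates while marking it through Day 21.

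No new data are needed, since CO, the dated bags and the marijuana questions are already collected. There are two costs. Fewer participants will be supported as cigarette-free. Some readings above 5 may come from smoked marijuana, which a past-month question cannot date, so the discordance count qualifies the filter data and does not replace them.
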